# 13.4.1 Study Subjects and Demographics

# 13.4.1.1 Disposition and Withdrawals

The numbers of subjects treated, completing, and withdrawing, along with reasons for withdrawal, will be tabulated overall, by subject type, and by injection procedure. The number of subjects in each analysis population will be reported.

#### 13.4.1.2 Protocol Deviations

Protocol deviations will be identified and summarized or listed as appropriate.

#### 13.4.1.3 Demographics and Other Baseline Characteristics

These analyses will be conducted for all analysis populations.

Demographic variables will include age, sex/gender, height, and weight. Information on race and ethnicity will be collected for any eventual analysis of differences in response to CNTX-4975-05, in accordance with local regulatory requirements. Baseline subject characteristics will include medical history, including confirmation of OA diagnosis and time since diagnosis, and physical examination findings.

Prior and concomitant medications will be summarized, by the number and percentage of subjects taking each medication, classified using World Health Organization Drug Dictionary Anatomical Therapeutic Chemical classes and preferred terms.

# 13.4.2 Exposure and Compliance

All subjects will receive up to 1 CNTX-4975-05 injection in each knee, at the study site under the surveillance of appropriate study personnel and, therefore, no compliance will be calculated. Injection procedure details and CNTX-4975-05 batch or lot number(s) will be recorded in the subject's eCRF/electronic data capture (EDC) system and summarized or listed as appropriate.

# 13.4.3 Efficacy Analyses

Efficacy variables will be summarized and analyzed using the ITT population, unless otherwise specified.

# 13.4.3.1 Primary Analysis

The primary analysis will compare each experimental treatment regimen to the Breg Cooling Control Group using an equally-weighted, combined score calculated from the following 3 measures: 1) pain 30 minutes after CNTX-4975-05 injection (using the 0-4 scale of none, mild, moderate, moderately severe, and severe), 2) SS with the treatment regimen; and 3) IS with the treatment regimen, all assessed on the index knee. Ratios of the mean values of test/control will have 95% confidence intervals constructed for each treatment regimen versus the Breg Cooling Control Group. For a treatment regimen to be considered clinically acceptable, it must be no more than 30% worse than the Breg Cooling Control Group and the lower limit of the 95% confidence interval for the treatment regimen must be greater than 0.7. This analysis will be performed on the ITT population.

For analysis, satisfaction scores (SS and IS) and 30 minute pain after CNTX-4975-05 injection will be transformed to equivalent scales, and 30 minute pain after CNTX-4975-05 injection will be reverse-scored so that higher scores represent lower pain, in order to have the 3 components on the same scale before they are combined by summing the 3 scores for a composite score. A sensitivity analysis will be performed that creates a composite score using the original scales (with the pain scores still reverse-scored to ensure the direction of the effect remains the same), using the ITT population.

All other continuous secondary and exploratory efficacy endpoints will be summarized using descriptive statistics by subject type, experimental treatment regimen, and week/visit, as appropriate, and analyzed using a mixed-model repeated measures (MMRM) analysis or by analysis of covariance, as appropriate. Categorical endpoints will be compared between treatments using Pearson's chi-square or Fisher's exact test, as appropriate.

Safety analyses will be conducted using data from the safety population.

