#### 7.3 Study Site(s)

The study will take place at no more than 45 concurrent sites in the US, Germany, Spain and the United Kingdom. Each site is anticipated to screen a sufficient number of subjects to be able to enroll approximately 18 subjects. A study site with an acceptable recruitment rate and acceptable quality metrics may be allowed to recruit more subjects if other sites have low enrollment.

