#### 9.5 Method of Assigning Subjects to Treatment Groups

All enrolled subjects will be assigned to CNTX-4975-05. Assignment to unilateral or bilateral injections will be determined by the subject's OA pain and previous joint replacement status. The subject's joint treatment regimen will be based on the site at which the subject is enrolled.

Unilateral or Bilateral Injections: The study population will contain 3 types of subjects, with a targeted minimum of 150 subjects of each type:

- 1. Subjects with unilateral or bilateral OA of the knee, with one knee (the index knee) with moderate to severe pain (K-L grade 1-4) and the other knee (the contralateral knee) with no to mild pain. These subjects will receive an IA injection in the index knee only.
- 2. Subjects with bilateral OA of the knees, with both knees having moderate to severe pain (K-L grade 1-4, with worse pain in the index knee). These subjects will receive an IA injection into each knee (1 week apart). The index knee in these subjects is the one with the worst pain with walking. Where both knees have equal pain with walking, then the knee on the subject's dominant side will be designated the index knee.
- 3. Subjects who have unilateral or bilateral OA of the knee, with one knee with moderate to severe pain (the index knee [K-L grades 1-4]) and previous PJR or TJR in the other knee (the contralateral knee). These subjects will receive an IA injection into the index knee only.

Joint Treatment Regimen: Each site will be randomly assigned 1 of the 5 joint treatment regimens to be employed for ALL subjects at that site. The joint treatment regimens are listed in Section 9.3.2.

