#### 9.6 Blinding and Unblinding Treatment Assignment

This is an open-label study.

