#### 10.3.1.5 Investigator Satisfaction Questionnaire

The investigator will rate his or her satisfaction with the subject's study treatment.

The investigator will rate his or her satisfaction with the treatment procedure.

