#### 13.4 Statistical Analyses

This section presents a summary of the planned statistical analyses. A statistical analysis plan that describes the details of the analyses to be conducted will be written prior to database lock.

Unless otherwise indicated, all testing of statistical significance will be two-sided, and a difference resulting in a p value of  $\leq 0.05$  will be considered statistically significant. To control for the overall type I error rate, hierarchical testing based on fixed sequence procedure will be used. If statistical significance is declared for the primary analysis, formal hypothesis testing will be done for the secondary endpoints until a non-significant result is reached. All other p values from secondary and exploratory endpoints, after a non-significant p value is reached, will be considered nominal.

For analyses involving study site, if the number of subjects per site is small, sites may be pooled for analysis, or omitted from statistical models. The final determination will be made prior to database lock.

Summary statistics will be provided for the variables described below. For continuous variables, these statistics will typically include the number of subjects, mean, standard deviation (SD), median, minimum, and maximum. For categorical variables, these statistics will typically include the number and percentage of subjects in each category.

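### Regimens are randomised by site, but neither the primary ratio interval nor the categorical tests account for site as the randomised unit

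*Combined protocol and SAP*

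**What the plan says.** Section 9.5 sets the unit of randomisation: "Each site will be randomly assigned 1 of the 5 joint treatment regimens to be employed for ALL subjects at that site". The Synopsis and Sections 7.1 and 9.3.2 repeat the rule. Section 7.3 gives the expected site size: "Each site is anticipated to screen a sufficient number of subjects to be able to enroll approximately 18 subjects", with at most 45 sites open at the same time.

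The primary analysis in Section 13.4.3.1 states: "Ratios of the mean values of test/control will have 95% confidence intervals constructed for each treatment regimen versus the Breg Cooling Control Group". A regimen is clinically acceptable if it is no more than 30% worse than control and "the lower limit of the 95% confidence interval for the treatment regimen must be greater than 0.7". No variance estimator, model, site term or degrees of freedom is named.

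For other endpoints the same section says: "Categorical endpoints will be compared between treatments using Pearson's chi-square or Fisher's exact test, as appropriate". Every subject receives the same drug, so treatments here can only mean the regimens. Continuous secondary endpoints go to MMRM or analysis of covariance, again with no site term named.

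The only rule about site in the analysis is in Section 13.4: "if the number of subjects per site is small, sites may be pooled for analysis, or omitted from statistical models". That section also leaves details to a statistical analysis plan to be written before database lock.

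**The concern.** Site is nested within regimen, so differences between sites are part of the error of every regimen comparison. An interval built from subject-level variance leaves most of that error out. Pooling sites or dropping site from a model discards the unit that was randomised. A fixed site effect does not help, because it is confounded with regimen.

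Within-site correlation is plausible. Investigator satisfaction is one of three equally weighted components, and it is scored by the site's own investigator: "The investigator will rate his or her satisfaction with the subject's study treatment". Section 9.6 adds: "This is an open-label study". Oral pre-medication (Section 9.3.1) is at the investigator's discretion and ultrasound guidance (Section 9.3.3) is optional, so pain and subject satisfaction can also differ by site.

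At stake is the only decision rule for the primary objective. That rule also opens the fixed-sequence testing of secondary endpoints in Section 13.4.

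**Working it through.** The plan's 850 subjects are justified by safety requirements (Section 13.2). There is no power calculation, SD or ICC to reproduce.

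**Inputs**
- Subjects per site m = 18 (Section 7.3). 850/18 = 47 sites, or about 9 per regimen if sites are split equally (assumed). At the cap of 45 concurrent sites, 850/45 = 18.9 per site.
- ICC: not in the documents; 0.01 to 0.20 is assumed.
- Margin 0.7 and two-sided 95% interval (Section 13.4.3.1), so nominal error at the margin is 2.5%.

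**Formulas**
- Design effect D = 1 + (m − 1) × ICC
- Coverage of a subject-level 95% interval = 2Φ(1.96/√D) − 1
- Acceptance at a true ratio of 0.70 = 1 − Φ(1.96/√D)
- Chi-square type I error = P(χ² > c/D), with c = 3.84 (two regimens, 1 df) or 9.49 (all five, 4 df)

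Example at ICC 0.10: D = 1 + 17 × 0.10 = 2.70; 1.96/√2.70 = 1.193; coverage is 77% and acceptance at 0.70 is 11.6%.

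| ICC | D | Coverage | Acceptance at 0.70 (nominal 2.5%) | Chi-square, two regimens (nominal 5%) | Chi-square, five regimens (nominal 5%) |
|---|---|---|---|---|---|
| 0.01 | 1.17 | 93% | 3.5% | 7% | 9% |
| 0.05 | 1.85 | 85% | 7.5% | 15% | 27% |
| 0.10 | 2.70 | 77% | 11.6% | 23% | 48% |
| 0.20 | 4.40 | 65% | 17.5% | 35% | 71% |

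**Sensitivity to site size.** At 18.9 per site, acceptance at 0.70 is 3.6% / 7.7% / 12.0% / 18.0% for the four ICC values. At ICC 0.10 it is 9.9% with 850/60 = 14.2 per site and 15.5% with 850/30 = 28.3 per site.

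**Simulation of the ratio rule** (9 sites of 18 per regimen, normal data, coefficient of variation (CV) 0.3 assumed, Fieller limits, 20,000 runs per cell), for ICC 0.01 / 0.05 / 0.10 / 0.20:
- Subject level, true ratio 0.70: 3.5% / 7.5% / 11.8% / 17.5% accepted.
- Subject level, true ratio 0.65: 0.03% / 0.29% / 1.15% / 4.1%. At 0.60: 0.5% or less.
- Site-level t interval (9 + 9 − 2 = 16 df), true ratio 0.70: 2.5% / 2.6% / 2.6% / 2.4%.

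A second simulation (log-ratio delta-method interval, 19 per site, CV 0.25 and 0.35, 10,000 runs) gave about 3.7%, 7.5–7.8%, 11.9–12.5% and 17.9–18.6% at the margin. The site-level interval covered 94.7–95.4%.

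**Simulation of the chi-square test** (beta-binomial, 9 sites of 19 per regimen, success rate 0.6, 8,000 runs): 7.6% / 14.8% / 24.2% / 36.0% for two regimens. A site-level test gave 4.6–5.6%.

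**Which results would change.** With CV 0.35 (assumed) and 850/5 = 170 per regimen, the standard error of the log ratio is about 0.35 × √(2/170) = 0.038. The smallest observed ratio that passes at subject level is 0.7 × exp(1.96 × 0.038) = 0.754. At site level with ICC 0.10, 18.9 per site (D = 2.79) and t on 16 df (2.12), it is 0.7 × exp(2.12 × 0.038 × √2.79) = 0.801. Observed ratios between these two values pass one analysis and fail the other.

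**The case against.** For the primary analysis the protocol is silent; it does not state a wrong method. Section 13.4 calls itself a summary and defers detail to a later plan, and nothing in Section 13.4.3.1 rules out a site-level interval. This stands, so the narrowness is conditional on a subject-level calculation. Deferral is still a weak defence. The later plan is due only by database lock, the study is open-label, and Section 13.4.5 allows interim efficacy output at about 20%, 50% and 75% completion. The variance method could therefore be chosen after regimen results have been seen. The protocol already fixes the margin, the confidence level and the categorical tests.

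The categorical point has limits. Section 13.4.3.2 names the tests without saying what is compared; only Section 13.4.3.1 and the Synopsis refer to comparison between treatments. The responder endpoints in Section 13.1.2 are defined within subject type, and Section 13.4 gives no contrast for each step of the testing sequence. A five-regimen test is one reading, so the pairwise figures are the safer ones to use. The ICC range is also less well supported for responder endpoints, which are not listed as including investigator ratings.

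The higher ICC values may be too large even for the composite. If only investigator satisfaction clustered, and the three components were independent with equal variance, the composite ICC would be one third of the investigator-satisfaction ICC. A composite value of 0.10 would then need 0.30. Correlated components, or site differences in pain and subject satisfaction, would weaken that argument.

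Finally, the effect is concentrated near the margin. This is correct, but the 0.7 rule exists to decide exactly those cases.

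**Conclusion.** The concern holds. Sites are randomised, no provision brings between-site variance into the primary interval, and the named categorical tests ignore clustering. Confidence in the omission is high.

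Confidence in its size is moderate, because the ICC, the CV and equal allocation of sites are assumptions. If intervals are computed at subject level, the excess at the margin is small at ICC 0.01 and substantial from ICC 0.05 upward. Regimens well beyond the margin are still rarely accepted. For categorical endpoints compared between regimens, the inflation arises when the regimens do not differ, so false differences become more likely. Because this is the primary decision rule and the correction is one of wording, it should be made before any interim output or database lock.

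**What to change.** - **Primary analysis:** specify that the ratio and its 95% interval come from a model with a random site effect and small-sample degrees of freedom (for example Kenward-Roger), or from site means with a t interval whose degrees of freedom follow the number of sites (about 16 per comparison with 9 sites per regimen). Form the ratio limits by Fieller's method, or test the regimen mean minus 0.7 times the control mean. Other valid cluster-level methods would also serve; what matters is naming one in advance.
- **Site rule in Section 13.4:** state that site may not be omitted, or pooled across regimens, in any between-regimen comparison.
- **Categorical comparisons between regimens:** replace chi-square and Fisher with GEE using a small-sample correction, a generalised linear mixed model, or an analysis of site-level proportions.
- **Continuous comparisons between regimens:** include a random site effect in the MMRM and analysis of covariance models.

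The change is to protocol and analysis-plan wording and needs no extra subjects. The cost is precision. With 9 sites of 18 per regimen and CV 0.3 (assumed), a regimen truly 15% worse than control is accepted 99% / 95% / 85% / 65% of the time at ICC 0.01 / 0.05 / 0.10 / 0.20, against 99.9% / 99% / 98% / 94% with subject-level intervals. A truly equal regimen is still accepted more than 99% of the time.

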#### 10.1 Study Visits

### 10.1.1 Screening Visit, Day -14 to Day 1, Visit 1

The subject must be screened within 14 days before enrollment into the study. The following procedures will be performed at screening.

- Written informed consent
- Confirmation of knee OA K-L grade (1 to 4) of the knee, based on radiographs
- Confirmation of diagnosis of knee OA, based on ACR diagnostic criteria
- Inclusion/exclusion criteria
- Height and weight (BMI)
- History of cancer
- Knee pain with walking (during last 24 hours, assessed in the clinic using NPRS of 0-10)
- Demographics
- Medical history, including current OA medications (prescription and non-prescription medications) and treatment history (including noninvasive or previous invasive treatments)
- HADS
- FSS
- Knee circumference
- Complete physical examination
- ECG
- Clinical laboratory testing (fasting)
- Urine drug screen
- Urine pregnancy test
- Vital signs
- Issue paper diary to the subject with instructions on use and recording of background analgesic and rescue medication for index knee (or bilateral knee for subjects being treated for both knees)

### 10.1.2 Treatment, Day 1, Visit 2

As 2 cases of severe allergic reactions have occurred in the entire CNTX-4975 program, a crash cart and personnel certified in advanced cardiac life support (ACLS) should be immediately available. See section 11.2.1 for details.

The following procedures will be performed on Day 1.

- Knee pain with walking (during last 24 hours, assessed in the clinic using NPRS of 0-10)
- Partial physical examination
- ECG
- Urine drug screen
- Urine pregnancy test
- Vital signs (before and after injection of CNTX-4975-05). All subjects must be monitored for at least 30 minutes (or longer, as required by the protocol) after study drug injection to ensure that they do not have a hypersensitivity reaction/anaphylaxis. Vital signs (VS) are to be done standing and sitting within approximately 5 minutes before the injection of IP, and sitting-only vital signs within approximately 5, 15, and 30 minutes after the injection of IP.
- Injection site assessment (erythema, edema) before injection and 1 and 2 hours after the injection
- Review paper diary
- Sensory testing
- Subject assessment of procedure pain (using 0-4 scale)
  - o at rest prior to pre-medication;
  - o prior to IA lidocaine (without epinephrine);
  - o at rest 10 minutes (±2 minutes) after IA lidocaine (without epinephrine);

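### The primary test/control ratio is specified with no covariates and no site term, although whole sites are randomised and baseline walking pain and subject type are already collected

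*Combined protocol and SAP*

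**What the plan says.** Section 13.4.3.1, repeated in the Synopsis, defines the primary comparison of the composite score: "Ratios of the mean values of test/control will have 95% confidence intervals constructed". A regimen is acceptable only if "the lower limit of the 95% confidence interval for the treatment regimen must be greater than 0.7". No model, covariate, stratum or interval method is given. For the remaining continuous endpoints the same section does name models: they are "analyzed using a mixed-model repeated measures (MMRM) analysis or by analysis of covariance, as appropriate", again with no covariates listed.

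Section 9.5 makes the site the unit of allocation: "Each site will be randomly assigned 1 of the 5 joint treatment regimens to be employed for ALL subjects at that site". Section 7.3 allows "no more than 45 concurrent sites in the US, Germany, Spain and the United Kingdom". No stratification of the site randomisation by country or subject type is described.

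Walking pain (NPRS 0-10) is recorded at Screening and again on Day 1 before injection (Sections 2, 10.1.1 and 10.1.2). Subject type is known for everyone (Section 9.5), and country follows from the site. A 0-4 pain rating is taken "at rest prior to pre-medication" (Sections 10.1.2 and 10.3.3.3), on the same scale as the pain component of the composite.

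Section 13.4 describes itself as a summary. It leaves the details to a statistical analysis plan due before database lock, and allows sites to be pooled or left out of models.

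**The concern.** With about 9 sites per regimen, randomisation can leave arms noticeably different in baseline pain, subject mix or country. A ratio of plain means carries that difference directly into the number compared with 0.7. Subject-level covariates that could absorb part of it are already in the database, yet the decisive endpoint is the one for which no model is named. What is at stake is whether a regimen near the margin is accepted or rejected.

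Timing matters too. The study is open-label (Section 9.6), and Section 13.4.5 permits interim efficacy output at about 20%, 50% and 75% completion. A covariate set fixed only at database lock could be chosen with regimen results in view.

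**Working it through.** **Inputs from the documents.** At most 45 concurrent sites, 5 regimens, about 850 subjects, margin 0.7, two-sided 95% CI. Splitting equally (not stated) gives 45/5 = 9 sites and 850/5 = 170 subjects per regimen, and m = 850/45 = 18.9 subjects per site. There is no power figure to reproduce: Section 13.2 bases 850 on safety requirements and gives no SD, effect size or ICC.

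**Assumptions.** Composite CV 0.35; outcome ICC 0-0.10; covariate ICC 0-0.20; covariate-outcome correlation r 0.2-0.5; R² 0.1-0.3.

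1. *Chance imbalance in one covariate between two arms.* SD = sqrt[(2/170)(1 + (m-1)·ICC_x)]. This is 0.11, 0.18 and 0.23 covariate SDs at ICC_x 0, 0.10 and 0.20.

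2. *Effect on the ratio.* Shift from a 1.96-SD imbalance = 1.96 × SD × r × CV. The smallest case is 1.96 × 0.108 × 0.2 × 0.35 = 0.015. The largest is 1.96 × 0.232 × 0.5 × 0.35 = 0.080.

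3. *Subject type.* If the site share of bilateral subjects averages 35% with SD 10-20 points, the simulated SD of the arm difference is 0.069-0.104, and it exceeds 10 points with probability 0.14-0.33. If bilateral status shifts the composite by 0.3-0.5 SD, a 10-point gap moves the ratio by 0.10 × (0.3 to 0.5) × 0.35, about 0.01-0.02.

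4. *Country.* If a country had 5 of 45 sites, a given arm would have none with probability C(40,9)/C(45,9) = 0.309. At least one arm would have none with probability 1 - 9⁵/C(45,5) = 0.952. With 10 sites these fall to 0.080 and 0.372.

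5. *Precision of an arm mean.* Variance is proportional to ICC + (1-ICC)(1-R²)/m, if covariates explain only subject-level variance.
   - ICC 0.05: 0.1003 unadjusted, against 0.0953 (R² 0.1) and 0.0852 (R² 0.3). The SE falls by 2.5% and 7.8%.
   - ICC 0.10: 0.1476, against 0.1429 and 0.1334. The SE falls by 1.6% and 5.0%.

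6. *Where the verdict is sensitive.* If regimens are truly equal, the lower limit is about exp[-1.96 × 0.35 × sqrt((2/170)·DE)], with DE = 1 + (m-1)·ICC. That is 0.93 at ICC 0 and 0.88 at ICC 0.10 (DE 2.79), well clear of 0.7.

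7. *Simulation.* 9 against 9 sites, 19 subjects each, 3000 runs per scenario, CV 0.35, covariate ICC 0.10. Entries are the probability that the lower limit exceeds 0.7; at a true ratio of 0.7 the nominal value is 0.025.

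| Outcome ICC | r | 0.7: unadjusted, no site term | 0.7: covariate, no site term | 0.7: site-level | 0.7: site-level + covariate | 0.8: site-level | 0.8: site-level + covariate |
|---|---|---|---|---|---|---|---|
| 0.05 | 0.3 | 0.082 | 0.078 | 0.023 | 0.025 | 0.541 | 0.608 |
| 0.05 | 0.5 | 0.098 | 0.083 | 0.032 | 0.032 | 0.516 | 0.683 |
| 0.10 | 0.3 | 0.127 | 0.132 | 0.028 | 0.031 | 0.405 | 0.449 |
| 0.10 | 0.5 | 0.127 | 0.127 | 0.029 | 0.034 | 0.420 | 0.533 |

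The Monte Carlo SE at 0.025 is sqrt(0.025 × 0.975/3000), about 0.003. Here the covariate itself varies between sites, so adjustment also removes some between-site variance and can gain more than step 5. At ICC 0.05 and a true ratio of 0.8, the SD of the log ratio fell from 0.059 to 0.056 (r 0.3) and from 0.062 to 0.052 (r 0.5).

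**The case against.** A reader might infer that the plan has chosen raw means. It has not said so: it is silent, and Section 13.4 leaves details to a later plan. What can be said is that no adjustment is specified. The silence still matters, because the section names models for the other continuous endpoints and not for this one.

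A reader might also infer that the ratio is biased and that adjustment removes the bias. Under random assignment of sites, chance imbalance is part of the sampling variance, and an interval that respects sites already covers it. Adjustment reduces it. Nor do covariates repair an interval that ignores sites: in the table, false acceptance without a site term stays at about 0.08 (ICC 0.05) or 0.13 (ICC 0.10) with or without the covariate.

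Other limits stand:
- The 5-16% SE gain from sqrt(1-R²) applies only to subject-level variance, not to arm means under site randomisation.
- Entry walking NPRS is restricted to 5-9 (Section 8.2.1), and two of the three composite components are satisfaction ratings, so the correlation may be low.
- Country adjustment can rest on arm-by-country cells with no sites, and it spends between-site degrees of freedom.
- The 0-4 rest pain rating is timed before pre-medication, which is optional (Section 9.3.1). Its order relative to pre-cooling is not stated, so adjusting for it could remove part of the regimen effect.
- Subject type is partly addressed: a secondary endpoint assesses the composite by type (Section 13.1.2), and the primary uses the index knee, which is injected first in bilateral subjects. This does not adjust the primary ratio.

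**Conclusion.** The point holds in a limited form. The decisive ratio is specified without covariates or a site term in a design that randomises few sites, although walking NPRS and subject type are available before treatment. The resulting error is avoidable but modest: under the stated assumptions, a 1.96-SD imbalance in one covariate moves the ratio by 0.015-0.080, and adjustment trims the SE of an arm mean by about 2-8%. Regimens truly equal to control would pass either way. The difference shows at true ratios of about 0.7-0.8. With a site-level interval, adjustment raises the pass rate at 0.8 from 0.54 to 0.61 or from 0.52 to 0.68 (ICC 0.05, r 0.3 or 0.5).

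The documents give no CV, ICC, correlation or R², and do not state equal allocation of 45 sites, so these sizes are illustrative. The absence of any specified adjustment or site term does not depend on them.

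**What to change.** Prespecify the following in the protocol or an early analysis plan, before any regimen-level interim output:
- Estimate the primary regimen means from a mixed model of the composite with a random site effect and small-sample degrees of freedom (for example Kenward-Roger), and fixed effects for regimen, screening walking NPRS and subject type.
- Include country only in grouped form (for example US v Europe), and only if every arm has sites in each group.
- Use the 0-4 rest pain rating as a covariate only if it is recorded before cooling starts.
- Form the adjusted test/control ratio and its 95% CI from this model by the delta method or Fieller's method.
- Keep the unadjusted ratio with a site-level CI as a sensitivity analysis.

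The walking NPRS and subject type are already collected, so no new data are needed. The cost is slightly more analysis work and a few between-site degrees of freedom.
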